I. Study Design

- a. Prospective, noninvasive study to examine the individual and combined effects of OMT and Bio Electro-Magnetic Regulation (BEMER) Therapy on low back pain in adults.
- b. Study treatment location: All treatments and post treatment measurements will be performed in the osteopathic manipulative therapy laboratory at Lake Erie College of Osteopathic Medicine, Bradenton. [name] or [name], who are licensed osteopathic physicians, will be on call in the vicinity of the treatment location, however not necessarily in the room of treatment.
- c. Data Collection
 - i. After written consent is obtained, the study coordinator will assign the participant a randomized study number to de-identify the participant.
 - ii. To achieve our project's goal, we will have 4 separate groups (OMT, BEMER, OMT+BEMER, and Placebo). OMT, BEMER, and placebo treatments will be performed by osteopathic medical students who have completed additional training given by a licensed osteopathic physician, to ensure uniform technique.
 - iii. To control for anchoring bias, subjects will be randomized into one of the four groups: OMT, BEMER, OMT+BEMER, and Placebo.
 - iv. Osteopathic Manipulation Diagnosis and Treatment Protocol

Osteopathic Diagnosis and Screening

1. Observe and Palpate Thoracic and lumbar muscles for TART (tenderness, asymmetry, restriction of motion, and tenderness) changes
2. Lumbar intersegmental diagnosis: used to guide treatment with muscle energy technique
3. Counterstrain Tenderpoint screening for the following muscles: psoas major, quadratus lumborum and piriformis- used to guide treatment with counterstrain technique
4. Sacrum diagnosis: Spring test at the base of the sacrum for palpation of flexed or extended dysfunction
5. Sacroiliac dysfunction: ASIS compression test – used to lateralize somatic dysfunction at sacroiliac joints

Osteopathic Treatment/Techniques

6. Regional thoracic myofascial release technique prone
7. Lumbosacral fascia myofascial release technique prone
8. Lumbar soft tissue unilateral pressure technique prone
9. Lumbar muscle energy technique seated or lateral recumbent

10. Psoas, piriformis, quadratus lumborum counterstrain technique supine
11. Sacrum balanced ligamentous tension technique supine
12. Lumbosacral/Pelvic fascia Myofascial Release technique supine

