1. BEMER is a therapeutic modality that deploys a biorhythmically defined stimulus through Pulsed Electromagnetic Field (PEMF). This stimulus has a targeted effect on the microvasculature, and the primary effect is an improvement in tissue microcirculation [3]. The positive effects of vasomotion on the microcirculation has been shown to result in significant increases in arteriovenous

oxygen difference, number of open capillaries, arteriolar and venular flow volume, and flow rate of red blood cells in the microvasculature [1, 2]. Therefore, BEMER can potentially be used in the treatment of LBP by improving microcirculation in muscular tissue.

- iii. Placebo (Light touch, and BEMER Sham): Treaters will place their hands lightly on the subject's lumbar paraspinal muscles in the supine and prone positions in the same area as where one would place your hands for lumbar MFR technique for the same amount of time as it would take to perform MFR in this area (approximately 5 minutes). However, no lifting or action will be done. In addition, the subject will lie down on the BEMER mat (as they would do during a BEMER session), but the device will not be activated. This treatment will be used as a control.
- e. The research assistants will individually coordinate experimental times with the subjects. A licensed osteopathic physician will be in the vicinity of the treatment location at all times while treatments are being given.
- f. OMT, BEMER, and placebo will be performed by osteopathic medical students who have completed additional training given by a licensed osteopathic physician to ensure uniform technique. A licensed osteopathic physician will be in the vicinity of the treatment location at all times while treatments are being given.
- g. All data collection logs will be de-identified of personal information and only contain the randomized participant ID number linking the participant to the data collected. [name], who is one of the research coordinators, will be the data analyst.
- h. The identifying information will be maintained by the principal investigator in a locked cabinet, which he alone has access to.

II. Study Procedures and Timeline

- a. Study duration

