 - xxi. Asthma exacerbations within the last 4 weeks
 - xxii. Immunosuppressive therapy as a consequence of organ transplantation
 - xxiii. Immunosuppressive therapy as a consequence of allogeneic cellular transplants or bone marrow stem cell transplantation

- xxiv. Other conditions often requiring immunosuppressive therapy
- xxv. Anticoagulant therapy
- xxvi. Known sensitivity to the carotid sinus reflex
- b. Subjects will be screened for eligibility based on the inclusion and exclusion criteria described above at the point of subject consent. No protected health information will be collected from subjects who are not eligible to participate in the study.
- c. If subjects develop any of the above issues during the course of the study, they will be removed from the study without penalty and will still receive compensation.

III. Definition of treatment failure or subject removal criteria

- a. Subjects who do not adhere to the full treatment regimen will be removed from the study.
- b. Subjects who experience any adverse effects from treatment, as determined by a licensed osteopathic physician, will be immediately removed from the study. However, we do not anticipate any adverse effects during the study.

Risks and Benefits

I. Risks

- a. Anticipated medical risks**
 - i. After OMT, muscle tenderness and generalized discomfort may be noted 24-48 hours after treatment in a small number of patients.
 - ii. There is little empiric data about the “hazards” to patients of student-performed procedures. Further, this study does not employ any inherently forceful techniques.
 - iii. There are no anticipated adverse effects associated with BEMER therapy.
- b. Steps taken to minimize the risks**
 - i. All Osteopathic Medical students performing osteopathic manipulation will receive additional special training by a licensed osteopathic physician, member of the LECOM-Bradenton OMM Department, and will disclose their true identity to the subjects to avoid any misconceptions that they are licensed physicians. Student-treaters will be critiqued by a physician until they are approved to perform OMT on the subjects.
 - ii. A licensed osteopathic physician will be in the vicinity of the treatment location at all times a treatment is being given.

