 - iii. The operation of the BEMER Pro Set will be done by students, who will be trained by a BEMER representative. The BEMER representative will ensure students are well trained in the operation of the device. In addition, the Principal Investigator will also be available during the training and throughout the study duration to assist the students.
 - iv. There are no funds designated to compensate subjects for injury. The principal investigator will work with injured subjects to provide them with further information to the best of his ability.

c. Plan for reporting adverse events

- i. All serious or unanticipated adverse events must be reported to the LECOM IRB promptly.
- ii. All protocol amendments will be submitted to IRB for approval, with the exception of changes that must be made in order to eliminate any imminent risk of harm to subjects or to others. In this circumstance, the investigator will act to eliminate the immediate risk but must subsequently submit an appropriate protocol amendment and await approval before proceeding with the revised protocol.

II. Benefits

a. Description of probable benefits

- i. Subjects may experience a decrease in low back pain. This can translate to healthy and natural ways to improve quality of living in patients with disabling low back pain. Individually, patients could see significant increases in quality of life.
- ii. With regards to society, this study could provide patients with an efficient and inexpensive way to alleviate many of the disabilities that are associated with living with low back pain.

Consent Process and Privacy Protection

I. Consent Process

- a. Participants will be introduced to the study through classroom announcements and recruitment emails. If they decide to participate we will provide participants with a written informed consent form (Appendix B) for them to read. In addition, a researcher will thoroughly explain the study to them to ensure that the subject is willing to participate in the experiment. The participant will then sign the form after comprehension is assessed via verbal reiteration and opportunity has been provided for questions.

II. Privacy Protection/Confidentiality

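### Treaters necessarily know which sessions are sham and every outcome is self-rated, but blinding covers only the analysis and no approval step or neutral script is stated for BEMER or sham delivery

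*Combined protocol and SAP*

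**What the plan says.** **Who delivers and who trains.** Methodology I.c.ii states: "OMT, BEMER, and placebo treatments will be performed by osteopathic medical students who have completed additional training given by a licensed osteopathic physician". The same statement recurs in I.f, II.a.i and II.c.ii, with uniform technique as its purpose. Risks and Benefits I.b.iii adds, for the device: "The operation of the BEMER Pro Set will be done by students, who will be trained by a BEMER representative". It continues: "The BEMER representative will ensure students are well trained in the operation of the device", and says that "the Principal Investigator will also be available during the training and throughout the study duration to assist the students".

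**Who approves.** Risks and Benefits I.b.i says: "Student-treaters will be critiqued by a physician until they are approved to perform OMT on the subjects". No equivalent sentence is given for BEMER or for placebo.

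**What the sham is.** In Methodology I.d.iii the hands rest on the lumbar muscles: "However, no lifting or action will be done". The subject also lies on the mat, "but the device will not be activated".

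**Outcome and blinding.** The primary outcome (III.a.i) is questionnaire ratings before and after treatment. The instruments are the SF-12, a pain VAS and the Oswestry questionnaire (Appendices C to E), all completed by the subject. Section III.b blinds the outcome analyses and claims that this removes bias from investigator self-interest. It does not mention treaters.

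**The concern.** The person giving a session has to know whether the mat is on and whether the touch is real. That person then talks with the subject, session after session, and the subject later supplies the rating. What the treater conveys about likely benefit, progress or the state of the device can therefore reach the outcome directly, and can differ by arm. An analyst blind to group receives ratings that already contain the effect.

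The plan's safeguards sit elsewhere. Formal approval of treaters is written for manipulation only. The assurance for BEMER concerns operating the device. The two sham components, on which every active-versus-placebo comparison rests, have no stated approval step. At stake is whether a difference from placebo can be attributed to the treatment rather than to how the session was presented.

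**Working it through.** **Step 1. Amount of contact (Methodology II.a.i).** OMT: 3 per week × 3 weeks = 9 sessions. BEMER: 5 per week × 3 weeks = 15 sessions. Placebo follows the same intervals. Methodology I.b allows the supervising physician to be outside the room.

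**Step 2. Training and checks, side by side.**

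| Component | Training stated | Competence check stated |
|---|---|---|
| OMT | Physician; osteopathic course director and clinical faculty (Methodology I.c.v) | Physician critique until approved |
| Active mat | Physician (additional training); BEMER representative (device operation) | Representative, for device operation |
| Inactive mat | Physician (additional training for placebo) | None stated |
| Light touch | Physician (additional training for placebo) | None stated |

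The one visible rule on what treaters tell subjects is that they must disclose that they are not licensed physicians (Risks and Benefits I.b.i). Nothing visible covers expected benefit, progress, device status or which procedure is sham.

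**Step 3. Sample size.** The only design figure is about 10 subjects for the paired tests (III.a.ii). Read as per group, 4 × 10 = 40, which matches the 40 budgeted under Payment and Costs II.a. No alpha, power, effect size or SD is given, so the 10 cannot be derived.

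**Step 4. Illustration of what a bias would do.** Every bias input here is an assumption. Take a shift of 0.2 to 0.5 SD in favour of the active arms. One route to that range is 5 to 10 mm on the 100 mm VAS with an SD of 20 to 25 mm: 5/25 = 0.2 and 10/20 = 0.5. Set the true effect to zero, n = 10 per arm, and two-sided alpha to 0.05.

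- *Two-sample t-test, one active arm against placebo:* 18 degrees of freedom, noncentrality d × √(n/2) = d × √5. At d = 0.2 this is 0.447 and at d = 0.5 it is 1.118.
- *Planned one-way ANOVA, all three active arms shifted:* F with 3 and 36 degrees of freedom, noncentrality n × Σ(mean − grand mean)² = 10 × 0.75d² = 7.5d². This gives 0.300 and 1.875.
- *Planned ANOVA, only the two BEMER arms shifted:* noncentrality 10 × d², giving 0.400 and 2.500.
- *Planned paired t-test within a group:* 9 degrees of freedom, noncentrality d × √10, with d in SDs of change. This gives 0.632 and 1.581.

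| Assumed bias | Two-sample t | ANOVA, three active arms | ANOVA, two BEMER arms | Paired t |
|---|---|---|---|---|
| 0 | 5.0% | 5.0% | 5.0% | 5.0% |
| 0.2 SD | 7.1% | 6.6% | 7.2% | 8.8% |
| 0.3 SD | 9.7% | 8.8% | 10.2% | 13.6% |
| 0.5 SD | 18.5% | 16.7% | 21.2% | 29.3% |

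The zero row is the nominal level. The paired column uses a different unit, so it should not be compared row by row with the others.

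**The case against.** The strongest reply has five parts.

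**Treater unblinding is unavoidable in manual therapy.** True. It does not make neutral wording or a check of sham delivery unavailable.

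**The students are not checked only on OMT.** A reader might infer that they are, but I.b.iii has the representative make sure they are competent with the device and keeps the principal investigator available. What stands is narrower: no check independent of the representative is stated for BEMER, the stated check concerns operation rather than neutral delivery, and none is stated for the sham components.

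**The two training statements do not conflict.** A reader might see a contradiction between physician training and representative training. Both can be true if one teaches delivery and the other teaches the controls. A clarification is enough.

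**The approval step is a safety measure.** It sits among the steps to reduce risk, so its silence on light touch is not surprising. That explains the gap but does not fill it.

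**The mechanism is inferred.** A reader might suppose that the same student sees the same subject throughout, or that the representative passes on commercial enthusiasm. The documents say nothing about which student treats whom, and they describe neither the representative's interests nor any message. Nor could the representative explain a bias in OMT against placebo, since OMT is taught by faculty. The concern needs none of this: it needs only a treater who knows what the session is.

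There is also a limit on what can be checked. The consent form and part of the roles list were not in the text reviewed, so statements about absence apply to the visible text only.

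**Conclusion.** The point holds in a limited form. Treaters necessarily know active from sham. The plan does not say so; it follows from the description of the sham. All outcomes are self-rated, and the stated blinding acts after any session-level bias has entered. No approval step is stated for the light touch or the inactive mat, and device competence rests on the BEMER representative alone.

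The size is unknown. The figures of about 7% to 19% for the two-sample t-test show what an assumed bias of 0.2 to 0.5 SD would do with 10 per arm and no true effect. A reader might take them as this trial's error rate. They are not: no bias or SD is documented, a bias near zero is possible, and the two-sample test is not the planned between-group test. The planned ANOVA gives a similar range, about 7% to 17% with all three active arms shifted.

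The change is worth making before enrolment because analysis cannot remove the bias afterwards.

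**What to change.** 1. In Methodology III.b, state that treaters are unblinded, and limit the claim that bias is eliminated to the analysis.
2. Within the physician training already planned (Methodology I.c.ii, I.f, II.a.i, II.c.ii), train all students on a short neutral script for greeting, set-up and closing talk. Keep it the same in all four arms apart from technique instructions, with nothing said about expected benefit, progress, device status or which procedure is sham. A single word-for-word script for the whole session would not work, because muscle energy requires spoken requests to the subject.
3. Extend the critique-until-approved step in Risks and Benefits I.b.i to the light-touch, active-mat and inactive-mat sessions.
4. Clarify in Risks and Benefits I.b.iii that the representative teaches device operation only and the physician teaches session delivery.

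The cost is a short script, slightly longer training and less natural conversation, with no extra staff. Non-verbal cues would remain, so the bias would be reduced rather than removed.

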Appendix A: Recruitment email

The LECOM Student American Academy of Osteopathy (SAAO), is conducting a study, and we would like to welcome all LECOM faculty, staff, and students to participate. The study will evaluate the individual and combine impact of osteopathic manipulative treatment (OMT) and Bio Electro-Magnetic Regulation (BEMER) Therapy on low back pain.

This study will take place over a three-week period. Each subject in the OMT group will receive treatment 3 times per week for a period of 3 weeks. Subjects in the BEMER groups will receive treatment 5 times per week for a period of 3 weeks. Each subject in the OMT+BEMER group will receive OMT 3 times per week and BEMER therapy 5 times per week for a period of 3 weeks. Subjects will complete brief questionnaires regarding low back pain and quality of life before the beginning of study and will complete the same questionnaires following the completion of the three week treatment. Each treatment will be individually scheduled with your assigned study coordinators. Each treatment session will last approximately 10-30 minutes. You will be compensated with a \$50 gift card for your time.

If you are interested and would like to learn more about the study, please contact [name] (Study Coordinator) at [contact] for more information. Thank you for your consideration in helping with this very important research.

Appendix C:
SF-12 Health Survey

SF-12 HEALTH SURVEY (STANDARD)

INSTRUCTIONS: This questionnaire asks for your views about your health. This information will help keep track of how you feel and how well you are able to do your usual activities.

Please answer every question by marking one box. If you are unsure about how to answer, please give the best answer you can.

1. In general, would you say your health is:

				
Excellent	Very good	Good	Fair	Poor

The following items are about activities you might do during a typical day. Does your health now limit you in these activities? If so, how much?

	Yes, Limited A Lot	Yes, Limited A Little	No, Not Limited At All
2. Moderate activities , such as moving a table, pushing a vacuum cleaner, bowling or playing golf			
3. Climbing several flights of stairs			

During the past 4 weeks, have you had any of the following problems with your work or other regular daily activities as a result of your physical health?

	Yes	No
4. Accomplished less than you would like		
5. Were limited in the kind of work or other activities		

During the past 4 weeks, have you had any of the following problems with your work or other regular daily activities as a result of any emotional problems (such as feeling depressed or anxious)?

	Yes	No		
6. Accomplished less than you would like				
7. Didn't do work or other activities as carefully as usual				
8. During the past 4 weeks , how much did pain interfere with your normal work (including both work outside the home and housework)?				
				
				
				
Not at all	A little bit	Moderately	Quite a bit	Extremely

These questions are about how you feel and how things have been with you during the past 4 weeks. For each question, please give the one answer that comes closest to the way you have been feeling. How much of the time during the past 4 weeks –

[figure not shown]
	All of the Time	Most of the Time	A Good Bit of the Time	Some of the Time	A Little of the Time	None of the Time
9. Have you felt calm and peaceful?						
10. Did you have a lot of energy?						
11. Have you felt downhearted and blue?						
12. During the past 4 weeks , how much of the time has your physical health or emotional problems interfered with your social activities (like visiting with friends, relatives, etc.)?						

	All of the time	Most of the time	A Good Bit of the time	Some of the time	A little of the time	None of the time
--	------------------------	-------------------------	-------------------------------	-------------------------	-----------------------------	-------------------------

Appendix D:

Visual Analog Scale

The Visual Analog Scale (VAS) is a 100-millimeter line with “no pain” on one end and “pain as bad as it can be” at the other end. This scale is a very simple form of assessment. Patients are expected to mark on the line the amount of pain they are experiencing.

Appendix E: Oswestry low back pain questionnaire

Instructions

This questionnaire has been designed to give us information as to how your back or leg pain is affecting your ability to manage in everyday life. Please answer by checking ONE box in each section for the statement which best applies to you. We realise you may consider that two or more statements in any one section apply but please just shade out the spot that indicates the statement which most clearly describes your problem.

section 1 - pain intensity

- I can tolerate the pain I have without having to use pain killers
- the pain is bad but I manage without taking pain killers
- pain killers give complete relief from pain
- pain killers give moderate relief from pain
- pain killers give very little relief from pain
- pain killers have no effect on the pain and I do not use them

section 2 - personal care (washing, dressing, etc)

- I can look after myself normally without causing extra pain
- I can look after myself normally but it causes extra pain
- it is painful to look after myself and I am slow and careful
- I need some help but manage most of my personal care
- I need help every day in most aspects of self care
- I do not get dressed, wash with difficulty and stay in bed

section 3 - lifting

- I can lift heavy weights without extra pain
- I can lift heavy weights but it gives extra pain
- pain prevents me from lifting heavy weights off the floor, but I can manage if they are conveniently positioned, eg on a table
- pain prevents me from lifting heavy weights but I can manage light to medium weights if they are conveniently positioned
- I can lift only very light weights
- I cannot lift or carry anything at all

section 4 - walking

- pain does not prevent me walking any distance
- pain prevents me walking more than 1 mile
- pain prevents me walking more than 1/2 mile
- pain prevents me walking more than 1/4 mile
- I can only walk using a stick or crutches
- I am in bed most of the time and have to crawl to the toilet

section 5 - sitting

- I can sit in any chair as long as I like
- I can only sit in my favourite chair as long as I like
- pain prevents me from sitting more than 1 hour
- pain prevents me from sitting more than 1/2 hour
- pain prevents me from sitting more than 10 minutes
- pain prevents me from sitting at all

section 6 - standing

- I can stand as long as I want without extra pain
- I can stand as long as I want but it gives me extra pain
- pain prevents me from standing for more than 1 hour
- pain prevents me from standing for more than 1/2 hour
- pain prevents me from standing for more than 10 minutes
- pain prevents me from standing at all

section 7 - sleeping

- pain does not prevent me from sleeping well
- I can sleep well only by using tablets
- even when I take tablets I have less than six hours sleep
- even when I take tablets I have less than four hours sleep
- even when I take tablets I have less than two hours sleep
- pain prevents me from sleeping at all

section 8 - sex life

- my sex life is normal and causes no extra pain
- my sex life is normal but causes some extra pain
- my sex life is nearly normal but is very painful
- my sex life is severely restricted by pain
- my sex life is nearly absent because of pain
- pain prevents any sex life at all

section 9 - social life

- my social life is normal and gives me no extra pain
- my social life is normal but increases the degree of pain
- pain has no significant effect on my social life apart from limiting my more energetic interests, eg dancing etc
- pain has restricted social life and I do not go out as often
- pain has restricted my social life to my home
- I have no social life because of pain

section 10 - travelling

- I can travel anywhere without extra pain
- I can travel anywhere but it gives me extra pain
- pain is bad but I manage journeys over two hours
- pain restricts me to journeys of less than one hour
- pain restricts me to short necessary journeys of less than 1/2 hour
- pain prevents me from travelling except to the doctor or hospital

from: Fairbank J C T, Couper J, Davies J B & O'Brien J P
Physiotherapy 1980; 66: 271-73

Research Roles and Support Documentation

All research project personnel, unless otherwise noted have completed, within the past two years, the on-line CITI training appropriate to their roles. Documentation of which are attached to this proposal.

- a. Principal Investigator
 - i. [name]., M.S., M.S. (Med Ed) CITI expiration: 01/03/2021
- b. Co-Investigator
 - i. [name], DO, MS CITI expiration: 05/07/2021
 - ii. [name], DO CITI expiration: 05/10/2021
- c. Graduate Student Researchers
 - i. Study Coordinator: responsible for consenting patients and maintaining study protocol
 - 1. [name] CITI expiration: 05/20/2021
